3.4.1.5 Subgroup Analyses of Primary Endpoint

Consistency of treatment effect measured by primary endpoint in the following subgroups will be investigated for the ITT population:

- Sex (male vs female)
- Baseline EDSS (< 5 vs ≥ 5)
- Number of prior NMO/NMOSD relapses (< 2 vs ≥ 2)
- Disease duration category (< 5 years vs ≥ 5 years)
- AQP4-IgG serostatus (positive vs negative) as determined at screening

The nominal p-value and 95% CIs of treatment effect will be provided for each subgroup analysis. Forest plots will be generated to visually present the consistency of treatment effect in different subgroups with overall treatment effect.

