4.8.3.4 Subgroup Analyses

Consistency of treatment effect measured by primary and key secondary efficacy endpoints in the following subgroups will be investigated as follows:

- Sex (male vs female)
- Baseline EDSS (< 5 vs ≥ 5)
- Number of prior NMO/NMOSD relapses (< 2 vs ≥ 2)
- Disease duration category (< 5 years vs ≥ 5 years)
- AQP4-IgG serostatus (positive vs negative) as determined at screening

The nominal p-value and 95% CIs of treatment effect will be provided for each subgroup analysis.

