2.4 Sample Size

Study CD-IA-MEDI-551-1155 is being planned to detect a target relative reduction of 60% in risk for time from Day 1 to onset of an adjudicated NMO/NMOSD attack on or before Day 197 with 90% power and $\alpha = 0.05$ (two-sided). A total of 67 AC-determined NMO/NMOSD attacks are required for the ITT population. Subjects will be randomized in a 3:1 ratio to receive either MEDI-551 or placebo within both AQP4-IgG seropositive and seronegative strata. The stratification ratio is anticipated to be approximately 80:20 with higher allocation to the seropositive cohort. If the sero-positive cohort has 80% of the attacks, the study will have approximately 82% power to detect the target relative reduction of 60%.

Two hundred and fifty-two subjects will be randomized. This sample size is based on a blinded review of the attack rate for the first 78 subjects to complete the RCP and on a simulation based on these subjects that indicates a 90% probability of achieving the required 67 AC-determined attacks with 252 subjects.

Within each AQP4-IgG stratum, randomization will also be stratified by region (Japan vs non-Japan). The number of Japanese subjects will be determined primarily by feasibility and will not depend on a minimum number of NMO/NMOSD attacks to be observed from Japanese subjects.

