3.4.1.3 Primary Efficacy Analysis

The following are the null and alternative hypotheses associated with the primary endpoint:

$$H_{01}: HR^+ = 1 \text{ vs } H_{11}: HR^+ \neq 1,$$

$$H_{02}: HR^{ALL} = 1 \text{ vs } H_{12}: HR^{ALL} \neq 1,$$

where HR^+ indicates the hazard ratio of AC-determined NMO/NMOSD attack for MEDI-551 relative to placebo in AQP4-IgG seropositive subjects. HR^{ALL} denotes the same quantity for the ITT population. The treatment effect in the seropositive cohort will be defined as the relative reduction in HR^+ ; ie, $100 \times (1 - HR^+)$. A value of $HR^+ < 1$ or a positive value of relative reduction will indicate the efficacy of MEDI-551 compared to placebo in the seropositive cohort. Similar interpretations will hold for HR^{ALL} . For the current study, the target treatment effect of 60% implies a hazard ratio (HR) of 0.4.

For the AQP4-IgG seropositive cohort, the treatment effect will be assessed using the Cox proportional hazards model with treatment indicator (MEDI-551 or placebo) as an explanatory factor; whereas for the ITT population, the model will also include serostatus as an additional explanatory factor. The HR of MEDI-551 versus placebo will be estimated together with its associated 95% CI. The SAS PROC PHREG will be used for fitting this model. Subjects who complete the Day 197 visit of the RCP or discontinue the study before Day 197 for reasons other than an AC-determined NMO/NMOSD attack will be censored in this model at the time of the Day 197/discontinuation visit.

An indicator variable for Japan versus non-Japan region will not be included in the Cox regression model due to the low number of anticipated Japanese subjects. An evaluation of consistency of treatment effect in Japanese subjects with that observed in the global study will be determined.

The data cutoff date for the primary analysis will be when the last subject completes the discontinuation visit following the 67th AC-determined attack, or after all subjects complete the RCP if 67 AC-determined attacks do not occur, or when the last subject completes the discontinuation visit following discontinuation of enrollment upon recommendation of the DMC based on evidence of efficacy and safety. Subjects who are in the RCP when a total of 67 AC-determined NMOSD attacks have occurred, or when enrollment is discontinued upon

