Appendix 1 Sample Size Calculation

The proposed study is being planned to detect a target relative reduction of 60% in risk for time (days) from Day 1 to onset of an AC-determined NMO/NMOSD attack on or before Day 197 with 90% power and $\alpha = 0.05$ (two-sided), assuming an unequal randomization ratio of 3:1 to MEDI-551 versus placebo. Using the following formula, a total of 67 AC-determined NMO/NMOSD attacks will be required:

$$E = \left[\frac{z_{1-\alpha/2} + z_{1-\beta}}{\ln(HR)} \right]^2 \times \frac{(r+1)^2}{r},$$

where $z_{1-\alpha/2}$ and $z_{1-\beta}$ are $100(1 - \alpha/2)^{\text{th}}$ and $100(1 - \beta)^{\text{th}}$ percentile of a standard normal distribution, $r = 3$ is the randomization ratio and $HR = \text{hazard ratio} = 0.4$.

Following the completion of the first 78 subjects in this study the sample size was reviewed. The attack rate of the first 78 subjects to complete the RCP was used to simulate the remaining subjects to estimate the probability of reaching the required 67 AC-determined attacks. The simulation showed that with a sample size of 252 subjects there is a 90% probability of reaching the required 67 AC-determined attacks.

The remaining text in this appendix describes the process of defining the original sample size of 212 subjects.

Assuming hazard rates of 1.5/year and 1.0/year for an NMO/NMOSD attack in the placebo arm for seropositive and seronegative groups, respectively, and using the following formula:

$$N = \frac{E}{\Pr(\text{Fail})},$$

a total of 212 (with an upward adjustment) subjects are expected to be enrolled in this study where

$$\Pr(\text{Fail}) = s_1 P_1 + s_2 P_2$$

is the weighted average of the failure probabilities P_1 and P_2 in seropositive and seronegative cohorts, respectively, with associated stratum specific weights $s_1 = 0.8$ and $s_2 = 0.2$. Recall that subjects will be enrolled to seropositive and seronegative cohorts in 80:20 ratio.

Furthermore, the probability of an attack within i^{th} cohort ($i = 1, 2$) is given by

$$P_i = (1 - w)p_{i0} + wp_{i1}$$

the weighted average of the failure probabilities p_{i0} and p_{i1} for placebo and MEDI-551 groups, respectively; $p_{i0} = 1 - e^{-\lambda_{i0}F}$, $p_{i1} = 1 - e^{-\lambda_{i1}F}$; $F = 197/365 = 0.54$ to indicate the 197 days (28 weeks) duration of the controlled portion of the study; note that based on the

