assumptions for this study, $\lambda_{10} = 1.5$, $\lambda_{11} = 0.6$, $\lambda_{20} = 1$ and $\lambda_{21} = 0.4$ and $w = \frac{r}{1+r} = 0.75$. Since the primary endpoint will be tested using the Cox proportional model, a simulation approach was used to investigate the power under alternative hypotheses mentioned above. Based on 5,000 simulations, the power for the overall and seropositive populations were observed as 94% and 91%, respectively. Moreover, the total required 67 events (212 subjects) were, on an average, distributed in seropositive and seronegative cohorts as 57 (168 subjects) and 10 (44 subjects) respectively.

The underlying hazard rate of time to an NMO/NMOSD attack in the seropositive placebo group is estimated based on a meta-analytic approach from several open-label cohort studies (see Table 7-1) in the absence of any placebo-controlled study in this population to date. These studies consisted of both seropositive and seronegative subjects and hence any finding related to hazard rate derived from these studies can be considered as an underestimation when applied for seropositive subgroup in the current study. Following are the 5 open-label studies considered with a total of 161 subjects:

Author	Title
Bedi et al	Impact of rituximab on relapse rate and disability in neuromyelitis optica. Mult Scler. 2011 Oct;17(10):1225-30
Costanzi et al	Costanzi C, Matiello M, Lucchinetti CF, Weinshenker BG, Pittock SJ, Mandrekar J, et al. Azathioprine: tolerability, efficacy, and predictors of benefit in neuromyelitis optica. Neurology. August 16, 2011;77(7):659-66.
Jacob et al	Treatment of neuromyelitis optica with rituximab: retrospective analysis of 25 patients. Muscle Nerve. 2008 Jan;39(1):87-90
Kim et al	Kim SH, Kim W, Li XF, Jung IJ, Kim HJ. Repeated treatment with rituximab based on the assessment of peripheral circulating memory B cells in patients with relapsing neuromyelitis optica over 2 years. Arch Neurol. 2011 Nov;68(11):1412-20.
Pittock et al	Pittock SJ, Lennon VA, McKeon A, Mandrekar J, Weinshenker BG, Lucchinetti CF, O'Toole O, Wingerchuk DM. Eculizumab in AQP4-IgG-positive relapsing neuromyelitis optica spectrum disorders: an open-label pilot study. Lancet Neurol. 2013 Jun;12(6):554-62.

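### The subgroup analyses are meant to show consistency of effect but plan no estimate or test of the difference between subgroup levels; the within-level p-values cannot supply it

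*SAP*

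**What the plan says.** Protocol 4.8.3.4 states the aim: "Consistency of treatment effect measured by primary and key secondary efficacy endpoints in the following subgroups will be investigated as follows". It lists sex, baseline EDSS, number of prior relapses, disease duration and screening serostatus, and promises a nominal p-value and 95% CIs per subgroup.

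SAP 3.4.1.5 repeats this for the primary endpoint in the ITT population ("The nominal p-value and 95% CIs of treatment effect will be provided for each subgroup analysis") and adds forest plots that set the subgroup effects against the overall effect. SAP 3.4.2.4 has the same output for the secondary endpoints, with four factors; serostatus is not among them.

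No section specifies an interaction term, a heterogeneity test or a ratio of effects between levels for any of these factors. A direct comparison of effects appears once, in SAP 3.4.1.4, where the Japan-to-global ratio of hazard ratios is offered as an optional assessment.

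**The concern.** Consistency means that the effect is the same in both levels of a factor. The p-value planned for each level addresses a different null, that the hazard ratio in that level is 1. Two levels with identical true effects will often fall on opposite sides of 0.05 because one has fewer attacks.

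Serostatus is where this matters most. The multiplicity procedure tests seropositive subjects and then the ITT population; none of its ten hypotheses concerns seronegative subjects alone. Seropositive subjects supply most of the attacks and can carry the ITT result, so the serostatus comparison is the main planned look at whether the effect extends to seronegative subjects. A non-significant p-value there is the likely result whether the drug works equally well or not at all.

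**Working it through.** **Inputs.** Hazard ratio: "the target treatment effect of 60% implies a hazard ratio (HR) of 0.4" (SAP 3.4.1.3). Allocation: "assuming an unequal randomization ratio of 3:1 to MEDI-551 versus placebo" (SAP Appendix 1). Attacks: "A total of 67 AC-determined NMO/NMOSD attacks are required for the ITT population" (SAP 2.4). Expected split of those attacks: "distributed in seropositive and seronegative cohorts as 57 (168 subjects) and 10 (44 subjects) respectively" (SAP Appendix 1). Placebo hazards of 1.5 and 1.0 per year for seropositive and seronegative subjects, and 197 days of follow-up (SAP Appendix 1). Two-sided 5% tests.

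**Step 1: reproduce the plan's figures.** Attacks = [(1.960 + 1.282)/ln 0.4]² × 16/3 = 66.75, so 67, as stated. With 80% of attacks seropositive (53.6), power = Φ(√(53.6 × 0.1875) × 0.916 − 1.960) = 0.828; the plan says about 82%.

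**Step 2: within-level significance at a common hazard ratio of 0.4, 67 attacks.** The same formula gives power A in seropositive and B in seronegative subjects. The strata are independent, so the chance of seropositive significance only is A(1 − B), and the chance that exactly one stratum is significant is A(1 − B) + B(1 − A).

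| Attacks (pos/neg) | A | B | Seropositive only | Exactly one |
|---|---|---|---|---|
| 57 / 10 | 0.850 | 0.241 | 0.645 | 0.681 |
| 53.6 / 13.4 | 0.828 | 0.306 | 0.574 | 0.627 |

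**Step 3: the same from expected attacks by arm.** With 168 + 44 subjects, expected attacks (placebo, active) are 23.3 and 34.9 seropositive, 4.6 and 6.4 seronegative. Taking the variance of each log hazard ratio as the sum of reciprocal counts gives standard errors of 0.268 and 0.612, powers of 0.93 and 0.32, and 0.93 × 0.68 = 0.63 for seropositive only. With 202 + 50 subjects (252 split about 80:20) it is 0.62. Cox simulations of 5,000 trials per scenario gave 59-63% for this pattern, and 61-65% for exactly one stratum significant. The range across methods for seropositive only is 57-65%.

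**Step 4: seronegative hazard ratio of 1.0.** Seronegative significance then occurs in 5%, so the pattern appears in 0.93 × 0.95 = 0.88 (168 + 44) or 0.96 × 0.95 = 0.92 (202 + 50); simulation gave 88-93%. With the fixed-attack powers of Step 2 it is 79-81%. On any of these bases the pattern is the majority outcome in both cases and separates them poorly.

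**Step 5: dependence on the assumed effect (assumed values).** For the two splits in Step 2, seropositive only falls to 50-61% at a common hazard ratio of 0.3 and 28-40% at 0.2. Attack splits for the other factors are not in the documents. Assuming 67 attacks and a hazard ratio of 0.4, exactly one level is significant in 47% at a 50:50 split and 74% at 90:10.

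**Step 6: what a between-level contrast would give.** Under a common hazard ratio of 0.4 an interaction test rejected in 3-4% of simulated trials.

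- *Precision.* From Step 3 (168 + 44), the standard error of the log ratio is √(0.268² + 0.612²) = 0.67, so the 95% limits lie a factor exp(1.96 × 0.67) ≈ 3.7 from the estimate. Simulation gave 3.6-3.9. With attacks fixed as in Step 2 the standard error is 0.71-0.79 and the factor 4.0-4.7.
- *Power for 0.4 versus 1.0.* It is 21-25% with attacks fixed as in Step 2. It is 33-37% by arm counts, and 30-35% in simulation, when seronegative attacks are allowed to rise to 18-21 because the drug does nothing there.

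**The case against.** The strongest reply is that nobody has said discordant p-values will be read as inconsistency. This is correct. A reader might infer that the plan would wrongly declare an inconsistent effect about 60% of the time; the documents do not support that. The p-values are labelled nominal, 95% CIs accompany them, and the forest plot is the tool the SAP names for displaying consistency. It compares effect sizes, and the fix keeps it.

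It is also fair that the levels of a factor are disjoint, so for the primary endpoint a reader could derive an approximate ratio and CI from the two reported hazard ratios. That shows how little the change asks; it does not put the contrast in the plan.

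Further points stand. The interaction test would miss a true 0.4-versus-1.0 difference by serostatus in most trials, because the limit is the number of seronegative attacks. The 202 + 50 scenario followed for 197 days yields about 82 attacks (69.9 + 12.5), beyond the 67 at which the plan ends the randomized period; this barely moves the discordance rate but raises the upper end of the interaction power. Serostatus is not a factor in SAP 3.4.2.4, and nothing was calculated for a secondary endpoint. An interaction term would not alter the primary testing hierarchy. Finally, the general rule in SAP 3.1 that model-based estimates carry CIs where appropriate may cover the Japan ratio, so its lack of an explicit CI is not relied on here.

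**Conclusion.** The gap is real and modest. The three sections pose a question about differences between levels and plan no statistic that estimates one. The within-level p-values do not answer it: at a common hazard ratio of 0.4, with the plan's hazards, allocation and follow-up, seropositive-only significance is expected in about 57-65% of trials, against about 90% if the seronegative hazard ratio is 1.0. The first figure is lower at stronger effects, and figures for other factors rest on assumed splits.

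Two stronger readings should be resisted. One is that the primary or key secondary conclusions are at risk: these analyses lie outside the ten-hypothesis alpha-controlled family. The other is that an interaction test would settle whether seronegative subjects benefit: at roughly 20-35% power it would not. The gain is that the uncertainty about the difference is estimated and shown.

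**What to change.** In SAP 3.4.1.5, SAP 3.4.2.4 and Protocol 4.8.3.4, for each factor listed in that section:

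- Add a treatment-by-subgroup term to the model already planned for the endpoint (Cox, logistic, ANCOVA or negative binomial).
- Report the between-level ratio of hazard ratios, odds ratios or rate ratios, or the difference in mean effects, with its 95% CI and the nominal interaction p-value.
- Keep the within-level estimates and CIs on the forest plot and drop the within-level p-values.
- State that the interaction test has low power (roughly 20-35% for serostatus at 0.4 versus 1.0, depending on the attack count), that the CI of the ratio is what is interpreted, and that a non-significant interaction is not proof of consistency.

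The cost is wording and one extra term per factor, with no new data. The downside is that wide intervals become visible, about a factor of 3.5-4 either way for serostatus and somewhat wider if seronegative attacks are as few as 10.

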3.4.1.6 Homogeneity of Attack Determination between Adjudication Committee and Investigators

The homogeneity of attack determination between the AC and investigator will be presented by the following quantities:

- The overall percent of agreement (OPA)
- The positive percent agreement (PPA)
- (Cohen’s) Kappa Statistic and 95% CI and p-value

Let a, b, c and d represents the count of subjects as shown in the table below; then, $OPA = 100 \times \frac{a+d}{a+b+c+d}$, $PPA = 100 \times \frac{a}{a+c}$, the negative percent agreement (NPA) $= 100 \times \frac{d}{b+d}$.

---		Investigator’s determination	
		Attack	Non-attack
AC-determination	Attack	a	b
	Non-attack	c	d

Appendix 6 provides the details of range of Kappa Statistic expected under the proposed study design.

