4.3.1.5 Independent Adjudication Committee

Three experts in NMO/NMOSD disease will constitute the independent AC. This committee has the mandate to evaluate each data set that is generated during the Assessment Visit and determine if an NMO/NMOSD attack occurred based on the clinical presentation, assessments, and the protocol-defined criteria for an NMO/NMOSD attack. The committee is completely independent and blinded to treatment assignments and/or to pertinent treatment

unmasking information (eg, B-cell counts, AQP4-IgG titers post-randomization) of study subjects, and to any decision made by the Principal Investigator regarding an NMO/NMOSD attack. The committee will use its judgement and clinical experience to make its determination based on the data provided. The committee will review the same data that are available to the Principal Investigator when he/she makes his/her determination about the attack. In exceptional cases, determined and justified by the committee as such, the committee can request to review additional data that is essential to make a determination. The committee's role, function and procedures are governed by a separate charter.

The data from all subjects who are assessed at an Assessment Visit due to a new symptom(s) or worsening of an existing symptom(s) related to NMO/NMOSD will be sent for adjudication by the AC regardless of whether the Principal Investigator has determined that an NMO/NMOSD attack has occurred. Furthermore, the AC will not receive information about which protocol attack criterion was met and the rescue medication utilized.

Determination of an NMO/NMOSD attack by the AC is for the purpose of determining which events will be included in the primary analysis. It will NOT affect the rescue therapy that a subject may receive.

Only subjects in whom the attack was determined by the AC will be given the option to enter the OLP.

In addition, the data set that was generated and used by the Principal Investigator to assess the symptom(s) that were determined not to be related to NMO/NMOSD in the RCP, will be delivered to the AC for a non-real-time review.

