Appendix 6 Kappa Statistic for Investigator and AC-determined Attack Agreement

Below is an investigation of the expected range of agreement between investigator and AC for NMO/NMOSD attack assessment for the current study. Figure 7-8 is based on 50,000 simulations. It is assumed that an AC-determined attack may be observed only if there is a site-determination of attack. X-axis presents the percentage of AC-determined attacks out of the total number of site determined attacks (positive percent agreement). A Kappa value of 1 (perfect agreement) is achieved when there are exactly 67 investigator-determined attacks which AC agrees in all cases. On the other extreme, when only 30% times AC agrees with the site, the Kappa value drops to less than 0.2 which is practically a high degree of statistical disagreement. The categories of Kappa value (according to [Landis et al.](#)) are shown on the right axis of the plot to determine the degree of agreement. It can be seen that based on the current design, one should expect as high as 75% of times AC should agree with site in order to get a Kappa value of 0.8 or higher. This also means that total number of investigator-determined attacks cannot be too high compared to target of 67 attacks, for example, higher than 90.

[figure not shown]

Figure 7-8 Agreement between Investigator and AC determination of Attacks

CI = Confidence interval

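### Investigator–committee agreement is built on a count of subjects that does not exclude those the adjudication committee never judged, which raises kappa and overall agreement

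*SAP*

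**What the plan says.** SAP section 3.4.1.6 cross-classifies the AC's determination against the investigator's: "Let a, b, c and d represents the count of subjects as shown in the table below". Cell a is attack for both, b is attack for the AC only, c is attack for the investigator only, and d is non-attack for both. Overall percent agreement (OPA) is (a+d)/n, positive percent agreement (PPA) is a/(a+c), negative percent agreement (NPA) is d/(b+d), and Cohen's kappa is added. Nothing limits the table to subjects who had an Assessment Visit.

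SAP Appendix 6 gives the range of kappa expected under the design. Its premise is "It is assumed that an AC-determined attack may be observed only if there is a site-determination of attack", that is, b = 0. Its upper anchor is "A Kappa value of 1 (perfect agreement) is achieved when there are exactly 67 investigator-determined attacks which AC agrees in all cases". Its benchmark is "as high as 75% of times AC should agree with site in order to get a Kappa value of 0.8 or higher", which it takes to mean that investigator-determined attacks should not exceed about 90. Its low anchor is a kappa below 0.2 when the AC confirms 30%. It does not state the number of subjects in the table. SAP section 2.4 gives the planned size: "Two hundred and fifty-two subjects will be randomized".

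Under Protocol sections 4.3.1.1 and 4.3.1.5, the AC decides on data sets generated at Assessment Visits. These include, for later review, symptoms that the investigator judged unrelated to the disease. Under Protocol section 3.1.1, a subject whose attack the AC does not confirm stays in the randomized period and may have a later attack that is confirmed.

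**The concern.** A subject with no Assessment Visit sends nothing to the AC. Placing that subject in cell d records an agreement on a case that the AC never judged. Kappa and OPA both rise with d, so the result depends partly on how many subjects had nothing to adjudicate.

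The subject unit has a second weakness. A subject with one rejected and one later confirmed site attack contributes a disagreement and an agreement but has only one cell, and the SAP gives no rule for choosing it. If the subject goes into a, the rejection disappears. PPA does not use d, but it is affected by this.

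What is at stake is how the statistic is read. Protocol section 4.8.7 specifies the kappa, and a reader will take it as agreement on cases that both parties judged.

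**Working it through.** **Inputs.** AC-determined attacks 67, b = 0 and 75% confirmation (Appendix 6); 252 subjects (SAP 2.4). Site attacks: 67/0.75 = 89.3, taken as 89, so c = 89 − 67 = 22.

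**Formula.** Kappa = (po − pe)/(1 − pe), with po = (a+d)/n and pe = [(a+b)(a+c) + (c+d)(b+d)]/n².

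**Reproducing the benchmark with all 252 subjects.** d = 252 − 89 = 163.
- po = (67 + 163)/252 = 0.913, so OPA is 91.3%.
- pe = (67×89 + 185×163)/252² = 36,118/63,504 = 0.569.
- Kappa = (0.9127 − 0.5688)/(1 − 0.5688) = 0.798. A 50,000-draw binomial simulation has mean 0.795.

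**Which d does the benchmark need?** With a = 67, b = 0, c = 22, kappa simplifies to 134d/(156d + 1,958). Setting this to 0.8 gives 9.2d = 1,566.4, so d is about 170 and n about 259. Kappa rises with d throughout, towards a ceiling of 134/156 = 0.86. The originally planned 212 subjects give 0.78.

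**The other anchors.** At 100% confirmation kappa is 1 for any d above 0. At 30%, site attacks are 67/0.30 = 223; with 252 subjects d = 29 and kappa is 0.09, consistent with below 0.2. A count of subjects must then hold at least 223 people, which 212 cannot.

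**Same 75% confirmation, assessed cases only.** The documents do not give the number of assessed cases, M; the values below 252 are assumptions. d = M − 89.

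| M | d | OPA | Kappa |
|---|---|---|---|
| 110 | 21 | 80.0% | 0.54 |
| 120 | 31 | 81.7% | 0.61 |
| 130 | 41 | 83.1% | 0.66 |
| 150 | 61 | 85.3% | 0.71 |
| 189 | 100 | 88.4% | 0.76 |
| 252 (all subjects) | 163 | 91.3% | 0.80 |

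PPA is 67/89 = 75.3% in every row. The confirmation needed for kappa of at least 0.8 is 86% at M = 120 and 82% at M = 150, against 76% with all 252.

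**Negative agreement.** With b = 0, NPA is 100% in every row. Section 3.4.1.6 now leaves b free; the SAP amendment history for 12 September 2018 records removal of the statement that b = 0. As an example, take b = 5 with 67 AC and 89 site attacks, so a = 62 and c = 27. At M = 120, d = 26, NPA is 26/31 = 83.9% and kappa 0.43. With all 252, d = 158, NPA is 158/163 = 96.9% and kappa 0.71.

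**The case against.** The strongest reply is that the SAP never says in words that unassessed subjects go into cell d. SAP section 3.1 bases percentages on non-missing observations where applicable, so section 3.4.1.6 could be read as already excluding subjects with no AC determination. Appendix 6 is an illustration with no stated N, and the 100% and 30% kappa values fit many choices of d. It is true that only the 75% figure discriminates on d. But that figure needs d near 170, and the 30% case needs at least 223 subjects in the table. The restricted reading fits neither well.

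A reader might infer that neither party ever looked at these subjects. The documents do not support that. Protocol Table 6 has the site assess every subject for new or worsening symptoms at each visit, and section 4.3.1.1 adds scripted calls every two weeks. Only the AC's determination is missing.

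Subject-level attack status under each definition is also a coherent comparison for a time-to-first-attack endpoint. It answers a different question from agreement on judged cases, and would need to be labelled as such.

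The size is also open to challenge. Because the AC also receives symptoms judged unrelated, assessed non-attacks could be numerous; with 100 of them kappa is 0.76, not far below 0.80. That stands.

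Finally, kappa is not the only check. The SAP has a Cox analysis of investigator-determined attacks and case-based relatedness concordance (Table 3.5.4-1), agreement on unrelated symptoms (3.7.2.1), a unanimous-adjudication sensitivity analysis (3.4.1.4) and rater reliability on sampled AC determinations (section 6). This limits the importance of the point. It also shows that the SAP uses cases or determinations as the unit elsewhere.

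**Conclusion.** The point holds. As written, section 3.4.1.6 does not exclude subjects without an AC determination, and the Appendix 6 benchmark is consistent with their being counted. Kappa and OPA are raised as a result. NPA is raised only if b is above 0. PPA is untouched by d but cannot represent a subject with both a rejected and a later confirmed site attack.

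At 75% confirmation, kappa moves from 0.80 to between 0.54 and 0.71 for 110 to 150 assessed cases, and to 0.76 with 100 assessed non-attacks. These values rest on an assumed number of assessed cases and on b = 0. That the all-subjects table is intended is an inference from the wording and from Appendix 6.

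A reader might go further and conclude that the adjudicated endpoint or the primary result is in doubt. The documents do not support this. No acceptance threshold is attached to kappa, and the primary test, alpha and the 67 events do not depend on it.

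**What to change.** In SAP section 3.4.1.6, make the unit the adjudicated Assessment Visit data set that has both an investigator and an AC determination. Count every such episode, so that a rejected and a later confirmed attack in one subject both appear. Give kappa, OPA, PPA and NPA with confidence intervals that allow for repeat episodes within a subject; a bootstrap that resamples subjects is one way. State whether symptoms the investigator judged unrelated enter the table.

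Restate Appendix 6 on that denominator, with b above 0 allowed and the assumed number of assessed cases shown.

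The cost is SAP wording, one reprogrammed table and a lower reported kappa. No new data are needed.
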